- Participants who do not show impaired swallowing safety on thin liquids in the videofluoroscopy (Penetration Aspiration Scale scores of 1 and 2) will be withdrawn from the study.
- Participants who have had, or have a planned neck dissection will be excluded.
- Individuals with tracheostomy *in situ* will be excluded from the study.
- Individuals with cognitive communication difficulties that preclude the understanding of the protocol or following study instructions will be excluded from the study.
- Due to the requirement to swallow stimuli containing starch based thickeners, which carry a significant carbohydrate load, individuals with Type 1 Diabetes will be excluded.
- Individuals with known allergies to latex, dental glue or barium will be excluded, due to the probability that these items will come into contact with the oral mucosa during data collection.
- Children and pregnant women will be excluded from the study due to the use of radiation
- Occupational exposure to radiation exceeding half the limit specified for Ontario exposed workers within the past 12 months.

These exclusion criteria will be confirmed using a self-report questionnaire form at the time of intake into the study (see standard operating procedures [SOP], provided as an additional study document). Any questions will be clarified through discussion with the research assistant responsible for participant intake, and, where necessary with the principal investigator.

Recruitment:

This is a preliminary study that will demonstrate feasibility for a future planned extension. We propose to recruit 10-12 participants. Potential participants will be identified by study Co-PIs [name] and [name] through the current radiation therapy clinics and base of tongue cancer caseloads at Princess Margaret Cancer Centre.

Stimuli:

An array of barium and non-barium stimuli has been developed for this study. These stimuli include thin, slightly-thick and mildly-thick liquids, defined using the International Dysphagia Diet Standardisation Initiative (IDDSI) gravity flow measures. The barium stimuli used for videofluoroscopy will be prepared using E-Z-Paque® barium in 20% w/v barium concentration with starch and gum-based thickening agents (Nestlé Resource® ThickenUp® and ThickenUp Clear®). The non-barium stimuli will be prepared using Nestle's Lemon Splash® lemon-flavoured water and the same starch and gum-based thickening agents

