Participants will be asked to swallow a series of thin, slightly-thick and mildly-thick barium stimuli 1 (3 boluses each of 5 stimuli, for a total of 15 boluses) in videofluoroscopy, with concurrent measurement of tongue-palate pressure. Videofluoroscopy will be performed at optimal temporal resolution (30 pulses/second) and captured at 30 frames/second. The stimuli will be presented in a randomized design, blocked by stimulus type. Participants will be allowed to take natural sized sips of each stimulus from cups containing 40 ml. Sip volume and mass will be calculated, by weighing the cups prior to and after the videofluoroscopic assessment.

Data Processing:

The tongue-pressure waveform will be segmented using an automatic segmentation algorithm developed previously in the PI's lab. Similarly, the videofluoroscopy recordings will be spliced into single bolus clips and the audio channel will be muted to remove cues that might bias rating. Blinded videofluoroscopy rating will then be performed in duplicate by trained raters in the [name] Lab following established procedures (see SOP provided as an additional study document). Discrepancies between raters will be flagged and resolved at consensus meetings, as required. These procedures will yield a

large number of parameters for each swallow. We will use established measures within our lab to collect and analyze measures related to kinematics and residue.

[figure not shown]
Follow-up phone calls: If deemed appropriate, the participant may be offered the opportunity to complete a follow-up component. For those willing to participate, this optional experiment will involve two follow-up telephone calls (at 2 weeks and 3 months following the videofluoroscopy) to determine compliance with use of thickened liquids recommended following the videofluoroscopy (see study instruments provided for questionnaires).

Data Analysis:

For Aim 1, we will compare hedonic ratings for the different stimuli using a univariate ANOVA. It is hypothesized that ratings will be significantly better for the thin and slightly thick stimuli compared to the mildly-thick stimuli, and that a preference will be seen for the gum compared to the starch thickened liquids.

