- c) Participants may experience some fatigue during the videofluoroscopy data collection session. Participants will be reminded that they should disclose any fatigue or discomfort to the research team, and that they are free to discontinue any particular session or to withdraw from the study at any time.
- d) Participants will receive additional exposure to radiation during the videofluoroscopy, in addition to their recent radiation treatment protocol. Based on a previous videofluoroscopic study that we have conducted in healthy adults, the study is expected to involve 118+/-18 seconds of radiation exposure (Molfenter & [name], 2013), with an associated dose estimate of <0.35 milliSieverts. Moro and Cazzani showed that this dose (0.35mSv) corresponds to a risk of 1 in 39,000 of developing a radiation-induced stochastic effect from a videofluoroscopy. We will use a 2-minute warning bell to alert the data collection team to exposure time, and will terminate the protocol at the first opportunity following the bell.
- e) Aspiration (entry of material into the airway) is a possible risk during the videofluoroscopic swallowing study that will be performed. This risk is always present for videofluoroscopic swallowing studies, which are intended to document the presence and severity of swallowing abnormalities, including (but not limited to aspiration). When aspiration is observed, standard procedures will be followed to encourage coughing and throat clearing to expel the aspirated material. The protocol will be terminated immediately. Any participant who experiences aspiration will be counseled regarding aspiration prevention strategies and aspiration-risk following the videofluoroscopy.
- f) Choking is an extremely unlikely event. However, in the event of choking, routine emergency procedures will be followed. All study personnel carry current CPR certification.

g) In the unlikely event that an incidental finding is noted on the videofluoroscopy (such as a diverticulum or a mass) the attending SRRL licensed speech-language pathologist will consult the on-call radiologist and generate a clinical report documenting the observation. These findings will be communicated with the participant as per usual clinical practice and follow up with their physician will be recommended.

Benefits

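### The planned 15 boluses sit almost on the 2-minute exposure stop, lost boluses fall on the last stimulus block, and neither balancing of block order nor a position term is described

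*Combined protocol and SAP*

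**What the plan says.** Section 3, Data Collection Session 2, plans "3 boluses each of 5 stimuli, for a total of 15 boluses" and adds: "The stimuli will be presented in a randomized design, blocked by stimulus type". The five stimuli are thin liquid, plus slightly-thick and mildly-thick liquids each made with starch and with gum. No scheme for balancing block position is described.

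Section 4, Risks (d), states that "the study is expected to involve 118+/-18 seconds of radiation exposure". The basis is given as "Based on a previous videofluoroscopic study that we have conducted in healthy adults". The bolus count of that earlier study, any time cap in it, and the meaning of ± are not given. The same item says "We will use a 2-minute warning bell to alert the data collection team to exposure time", and that the team "will terminate the protocol at the first opportunity following the bell".

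Risks (c) acknowledges that "Participants may experience some fatigue during the videofluoroscopy data collection session". Risks (e) adds another early stop: the protocol ends at once when aspiration is seen.

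Under Recruitment, "We propose to recruit 10-12 participants". Under Data Analysis, timing and residue are to be analysed by linear mixed models with stimulus as the factor, saliva as a covariate and possibly tongue pressure. There is no term for order or block position, and no rule for boluses that were planned but not obtained.

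**The concern.** The expected exposure is 2 s below the point at which the session is ended, so 15 boluses per participant is a target that a sizeable share of sessions may miss. Because stimuli come in blocks, a time stop does not thin the data evenly: it takes boluses from whichever stimulus is last. Late-session fatigue attaches to the same block.

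Random order protects each comparison on average over repetitions of the study, but there will be one realised set of 10–12 orders. If that set is lopsided, position effects and missing boluses fall more on some stimuli than on others. A model without position leaves this in the thin-versus-thickened and starch-versus-gum contrasts. The study is meant to show feasibility for an extension, so the share of sessions that yield all 15 boluses is also a result in its own right.

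**Working it through.** The plan states no completion rate, so there is no figure of its own to reproduce.

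**Inputs from the protocol.** Exposure 118 ± 18 s and a stop at 120 s (section 4, Risks (d)); 5 × 3 = 15 boluses in blocks (Session 2); 10–12 participants (Recruitment).

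**Assumptions.** ±18 is an SD; exposure T per session is about normal; 118 s describes a 15-bolus session; exposure is equal for each bolus within a session (T/15).

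**1. Reaching the bell.** P(T > 120) = 1 − Φ((120 − 118)/18) = 1 − Φ(0.111) = 0.456, or about 4.6 of 10 and 5.5 of 12 sessions. Other readings:
- lognormal 0.426, gamma 0.436, uniform on 100–136 s 0.444
- ±18 as a 95% half-width 0.414
- ±18 as a standard error (assumed n of 10–40) 0.486–0.493

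The range is about 41–49%. The result depends far more on the mean. With SD 18 and assumed means of 100, 110, 125 and 130 s, it is 13%, 29%, 61% and 71%.

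**2. Losing boluses, if the one in progress is completed.** At least j boluses are lost when T > 120 × 15/(15 − j).

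| j | Threshold (s) | Probability |
|---|---|---|
| 1 | 128.6 | 0.279 |
| 2 | 138.5 | 0.128 |
| 3 (whole last block) | 150.0 | 0.038 |
| 4 (reaches the block before) | 163.6 | 0.006 |

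Mean loss = 0.279 + 0.128 + 0.038 + 0.006 = 0.45 of 15. Per affected session it is 0.45/0.279 = 1.6. About 2.8 of 10 sessions are affected.

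**3. Losing boluses, if stopping is immediate.** All 46% lose something. Mean overrun = 18 × (φ(0.111) − 0.111 × 0.456) = 6.23 s. At 118/15 = 7.87 s per bolus, the mean loss is 6.23/7.87 = 0.79. Using T/15 and counting the interrupted bolus as wholly lost gives 0.456 + 0.279 + 0.128 + 0.038 + 0.006 = 0.91.

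**4. Which stimulus is last, if orders are drawn independently.** P(some stimulus is never last), n = 10: 5(0.8)^10 − 10(0.6)^10 + 10(0.4)^10 − 5(0.2)^10 = 0.537 − 0.060 + 0.001 − 0.000 = 0.48. For n = 12 it is 0.32. By simulation, some stimulus is last four or more times in 57% of allocations at n = 10. Last positions are as even as possible in only about 1% (n = 10) or 7% (n = 12).

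**5. Effect on the contrasts.** Within a participant, a block position has variance 2, and two positions have covariance −0.5. The difference therefore has variance 2 + 2 + 1 = 5. Over n participants the SD of the mean position difference between two stimuli is √(5/n): 0.71 blocks at n = 10 and 0.65 at n = 12. An unmodelled drift of δ per block adds noise with SD 0.71δ at n = 10. The documents give no value for δ.

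If position is fitted as a five-level factor, random orders inflate stimulus-contrast variance by about 13% against balanced orders at n = 10 (simulation, complete sessions). If it is fitted as linear, the inflation is roughly (0.5/90)/(2/10) = 3%. Here 0.5 = 5/10, and 90 is the within-participant position sum of squares (10 × 10 = 100) less about 10 explained by stimulus.

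**The case against.** Three stronger readings are tempting, and the documents do not support them.

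- **That 46% of sessions lose boluses.** 46% is the chance of reaching the bell. The stop comes at a point after the bell that is not defined. If the bolus in progress is finished, 28% lose a bolus and under 4% lose a whole block.
- **That the order is unbalanced.** The protocol says randomised and is silent on balance. Operating procedures are cited as separate documents and are not available here. The 48% and 57% apply only if orders are drawn independently.
- **That the stimulus comparisons are biased.** With randomised order, bell losses and fatigue favour no stimulus in expectation. What remains is chance imbalance, in a pilot, with an outcome effect that cannot be sized.

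It is also fair to say that the exposure figure is borrowed from healthy adults, possibly with a different bolus count or its own cap, so it may not describe this study. A mixed model already uses whatever boluses are obtained. The aspiration stop is arguably the more serious source of lost data, because it depends on the outcome and the bell does not.

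All of this narrows the point without removing it. The protocol itself offers 118 s as this study's expectation, beside a 120 s stop and a fixed plan of 15 boluses. Nothing described protects the single realised set of orders, and nothing says how shortfalls will be reported.

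**Conclusion.** The point holds in a limited form. On the protocol's own expectation, about 46% of sessions reach the bell (41–49% across readings of ±18). Between 28% and 46% lose at least one bolus, depending on how the stop is applied, with a mean loss of about 0.45 to 0.8 of 15. These figures rest on the SD, near-normal and 15-bolus readings of a healthy-adult figure, and they move substantially if the patients' mean differs. The losses come almost entirely from the last block.

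The consequence is added noise and uneven data by chance, not systematic bias. The imbalance figures are conditional on independent random orders, which the text permits but does not state. This is worth correcting before the first participant because the remedy is nearly free. It does not undermine the pilot.

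**What to change.** 1. Reconcile the 15-bolus plan in Session 2 with the exposure stop in Risks (d), and with the immediate stop on aspiration in Risks (e), which is a separate, outcome-dependent source of lost boluses. Which text changes is for the clinical team. State what happens to the bolus in progress at the bell.
2. State how block orders are generated, and take them from a balanced list. For example, a Williams design for five stimuli has 10 sequences, with each stimulus last exactly twice. It is exact for 10 completed sessions and near-balanced for 11–12 or after withdrawals.
3. Add block position to the stimulus mixed models.
4. Analyse all boluses obtained, and report the number by stimulus with the reason for each shortfall (bell, aspiration, fatigue, other).

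**Cost.** A pre-printed order list, one model term and one table, with no added exposure or visits. The small downside is 1 degree of freedom for a linear position term, or 4 for a categorical one, in a sample of 10–12.

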For Aim 2, blinded videofluoroscopy rating will be performed in duplicate, and discrepancies between raters will be flagged and resolved at a consensus meeting. The frequency of aspiration will be explored with the thin stimuli and compared to the prevalence of aspiration when thickeners are introduced using chi-square statistics.

We will model the impact of stimulus on two timing measures of pharyngeal bolus flow from the videofluoroscopy (i.e., a) the interval from the bolus passing the mandibular ramus until laryngeal vestibular closure; b) the interval from the bolus passing the mandibular ramus until entering the upper esophageal sphincter) and on measures of post-swallow residue (Normalized Residue Ratio Scale). The Saxon test results regarding oral dryness will be used as a covariate for all analyses, as illustrated in the Figure below:

A path analysis approach will be used to first identify differences in tongue pressure across stimuli

(Question 1). If confirmed, this potential modulator will be added to the Question 2 model as a covariate (Question 3). The planned analyses will involve linear mixed model repeated measures ANOVAs with a factor of stimulus.

For Aim 3, we will use qualitative methods to describe participant reports of adherence to the prescribed thickener. Information from the quality of life and performance status scales collected in session 1 will be used to inform our understanding of variations on patterns of thickener acceptance.

4. Risks and Benefits

Risks

The following risks will be disclosed to all participants prior to obtaining their consent to participate:

- a) Participants may experience local mucosal irritation from the glue on the adhesive strip used to attach the tongue-pressure bulbs for data collection. The glue usually wears off within 90 minutes following the conclusion of data collection. In the incidence that participants are unable to tolerate the attachment of the sensors, we will use the IOPI tongue bulbs to collect tongue measurements, and collect videofluoroscopic data using the same protocol.
- b) Participants may dislike the taste or texture of some of the thickened liquid stimuli in the study. Participants will be reminded that they are free to discontinue participation at any time.

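### Ending the session at the first observed aspiration conflicts with the 15-bolus plan, the thin-liquid retention rule, the aspiration comparison and the thickener benefit rule

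*Combined protocol and SAP*

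**What the plan says.** - **Stop rule.** Section 4, Risks, item e: "When aspiration is observed, standard procedures will be followed to encourage coughing and throat clearing to expel the aspirated material", followed by "The protocol will be terminated immediately". The item describes aspiration as material entering the airway and sets no PAS threshold. Item d uses similar words for the 2-minute exposure bell: the team "will terminate the protocol at the first opportunity following the bell". The natural reading is that the bolus sequence ends.
- **Planned data.** Section 3, Data Collection Session 2: "3 boluses each of 5 stimuli, for a total of 15 boluses". On order: "The stimuli will be presented in a randomized design, blocked by stimulus type".
- **Retention.** Section 3, Exclusion Criteria: participants whose thin-liquid swallows score only PAS 1 or 2 are withdrawn.
- **Analysis.** Section 3, Data Analysis, Aim 2: "The frequency of aspiration will be explored with the thin stimuli", to be "compared to the prevalence of aspiration when thickeners are introduced using chi-square statistics".
- **Use of the individual result.** Section 2 (Aim 1), Section 4 (Benefits) and Section 6: participants are advised to use thickened liquids that help them. Those who aspirate and do better on a tested thickener receive two cans.

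The protocol gives no rule for a participant stopped before thin, for the denominator of a shortened session, or for whether withdrawn participants' data are analysed.

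**The concern.** Four parts of the plan need the session to continue past the event that ends it. Three consequences follow from the rules alone, whatever the aspiration rates.

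1. Each participant gives at most one aspiration seen in the session, so nobody can be seen to aspirate on both thin and thickened liquid.
2. A participant who aspirates on a thickened block before the thin block has no thin score. The retention rule cannot be applied to that person. The Benefits rule, read literally, would still let that person receive a different thickener that was tested earlier, with no thin comparison.
3. For someone who aspirates on thin, every thickener was either tested earlier without a seen aspiration or never tested. On that outcome the result can favour a thickener or be missing, but cannot go against it.

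At stake are the advice given to individual patients and the amount of data behind the Aim 2 aspiration question.

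**Working it through.** **Plan's own figure.** 3 boluses × 5 stimuli = 15, which reproduces. The split of 3 thin and 12 thickened is inferred: 2 consistencies × 2 thickeners × 3 = 12. There is no stated alpha, power or aspiration rate to reproduce.

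**Assumptions.** Per-bolus aspiration rates p_t (thin) and p_k (thickened); independent boluses with equal risk across people; thin equally likely in each of five block positions; every aspiration seen in the session; no bell; nobody withdrawn.

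**Formulas under the stop.** Let q = (1−p_k)³ and S = 1 + q + q² + q³ + q⁴.
- Never receive thin: 1 − S/5.
- Thin-aspirators with no thickened bolus: 1/S. With all four thickeners tested: q⁴/S.
- All 15 given: 0.2(1−p_k)¹²(1−p_t)² + 0.8(1−p_k)¹¹(1−p_t)³.
- Expected thin boluses per person: (S/5)[1 + (1−p_t) + (1−p_t)²].

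**Worked case, 0.20/0.05.** q = 0.95³ = 0.857; S = 1 + 0.857 + 0.735 + 0.630 + 0.540 = 3.763.
- Never thin: 1 − 3.763/5 = 0.247, about 3 of 12 participants.
- Thin-aspirators with no thickened bolus: 1/3.763 = 0.266. All four tested: 0.540/3.763 = 0.144.
- All 15 given: 0.2 × 0.540 × 0.64 + 0.8 × 0.569 × 0.512 = 0.302.
- Thin boluses: 0.753 × 2.44 = 1.84 per person, or 22 for 12 people instead of 36.

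| Thin/thickened rate | Mean boluses | All 15 | Never thin | Thin-aspirators, no thickened bolus | Thin-aspirators, all four tested |
|---|---|---|---|---|---|
| 0.10/0.02 | 11.8 | 59% | 11% | 22% | 18% |
| 0.20/0.05 | 9.0 | 30% | 25% | 27% | 14% |
| 0.30/0.10 | 6.5 | 11% | 41% | 34% | 10% |
| 0.50/0.10 | 5.5 | 5% | 41% | 34% | 10% |
| 0.10/0.10 | 7.9 | 23% | 41% | 34% | 10% |
| 0.20/0.20 | 4.8 | 4% | 60% | 51% | 3% |
| 0.30/0.30 | 3.3 | 1% | 70% | 66% | 1% |

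**Individual judgement when thickeners do nothing (0.1/0.2/0.3).** Among thin-aspirators who had a thickened bolus, 100% show no thickened aspiration. With all 15 boluses given this would be (1−p_k)¹² = 28/7/1%. If 30% of aspirations are missed in the session and found at later rating, the 100% becomes 67/48/36%.

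**Pooled chi-square.** 20,000 simulated trials of 12 participants, Pearson test, boluses treated as independent, nobody withdrawn.
- Thickeners work (first four rows): power 54/61/52/88% with the stop, against 60/78/83/100% with all 15. Thin boluses fall from 36 to 29/22/15/12 and thickened from 144 to 112/85/62/54.
- No effect: rejection 3.7/5.1/5.5% with the stop, against 4.4/5.0/4.9% with all 15.
- If risk varies between people (logit SD 1.0-1.5), the stop shrinks the thin-minus-thickened difference by 15-35%, because high-risk people leave early.

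**Same null case with thin-safe participants' data dropped** (impaired taken to mean aspiration; people who never reached thin are kept): rejection is about 32/21/11% with the stop and 61/43/25% with all 15, in favour of thickeners. If half of those who do not aspirate on thin are retained for penetration, it is about 9/9/7% and 14/11/9%.

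**Counting boluses not given as safe.** At 0.20/0.05 the difference becomes 1.836 × 0.20/3 − 7.121 × 0.05/12 = 0.093 instead of 0.15, a 38% loss. Over the four working cases the loss is 19/38/57/67%.

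**The bell.** Section 4, item d: "the study is expected to involve 118+/-18 seconds of radiation exposure". Take the spread as an SD, 15 boluses of equal time, and a bolus under way as completed. The 15th bolus starts before 120 s if total time is below 120 × 15/14 = 128.6 s, and Φ((128.6−118)/18) = 0.72. So 72% would still get all 15 (mean 14.5) under the bell alone. The aspiration stop, not the bell, drives the loss.

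**The case against.** Stopping on aspiration is a legitimate safety choice. This is a feasibility pilot of 10-12 people whose aspiration rates are to be explored, and 15 boluses is a planned series already subject to the bell. The SOPs are separate documents not seen here and may say more. The Benefits rule is already limited to thickeners that were tested, and safer swallowing can include less penetration, so thickeners can still be told apart on that outcome. All of this stands. It limits the point to reconciling the rules; it does not reconcile them.

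The order is also an assumption: the protocol does not say how the blocks are randomised. If thin always came first, nobody would miss thin, but everyone seen to aspirate on thin would then have no thickened bolus at all.

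Stronger readings that the documents do not support:
- *The stop biases the pooled chi-square toward thickeners.* It is symmetric: thin tested before a thickened aspiration also looks safe. The simulation shows no material excess.
- *False positives are therefore not a worry.* That holds only if thin-safe participants stay in the comparison. Dropping them under the retention rule inflates rejection with or without the stop. The protocol does not say whether their data are dropped.
- *Penetration does not stop the session.* Item e has no PAS cut-off. Read literally, nearly every retained participant could trigger the stop.
- *The benefit rule can never be met.* A participant given thickened blocks before aspirating on thin can meet it.

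**Conclusion.** The conflict is real and worth fixing. The one-sided individual result and the missing rule for participants with no thin bolus follow from the text and need no assumed rate.

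The size is less certain, because every rate is assumed. Where thickeners work (0.10/0.02 to 0.50/0.10), with uniform thin placement, mean boluses fall to about 5.5-11.8 of 15, 11-41% never receive thin, and chi-square power falls to 52-88% from 60-100% if nobody is withdrawn. That power ignores clustering within participants, so it is optimistic. Of 12 participants, fewer than one would be expected both to aspirate on thin and to have had all four thickeners tested (0.51/0.63/0.45/0.59).

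For the pooled comparison, the stop costs precision and, if risk varies between people, attenuates the difference. Any inflation in favour of thickeners would come from the retention rule. The timing, residue and tongue-pressure mixed models can use unequal bolus counts and are outside this point.

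**What to change.** Keep the safety stop and amend the text around it:

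1. Define the trigger in item e by PAS score, so that it is clear whether penetration ends the session.
2. Call a thickener effective for a participant, and supply or recommend it, only if thin and that thickener were both tested in that participant. State that a thickener tested before a thin aspiration cannot have shown a seen aspiration.
3. Class a participant with no thin bolus as not assessable on thin, rather than withdrawing them as thin-safe.
4. Use boluses actually given as the denominator, and never count boluses not given as safe.
5. Keep withdrawn participants' thin data in the aspiration comparison. Present it descriptively, with boluses given per stimulus and the reason for stopping.
6. Balance block order: each stimulus twice in each position with 10 participants, two or three times with 11 or 12. The gain is small (the SD of the difference falls by about 0-9%) but free.

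The cost is protocol wording and a prepared sequence list, with no extra patients, boluses or exposure. Item 2 means fewer people are classed as helped by a thickener.

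Stopping only the current stimulus, and ending the session at a second aspiration or any clinical concern, is a clinical trade-off for the investigators and ethics board, not a required correction. In the four working cases it would cut never-thin from 11/25/41/41% to 1/4/11/11%, at the price of 0.07/0.28/0.57/0.67 more aspirations per participant.
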